21.0 Potential Benefits to Participants

21.1 Potential benefits.

Every participant who uses tobacco in the study will be given information about ways to access evidence-based treatment to help them stop smoking and will be given access to that treatment at no direct personal cost (apart from possible telephone charges for telephone-delivered care such as cessation counseling). UW-CTRI study coordinators will proactively offer smoking treatment options to patients, including tobacco quitline services (the Wisconsin Tobacco Quit Line for Wisconsin residents), referral back to their healthcare teams, or either standard or enhanced treatment in the CET (as randomly assigned). Given the known efficacy of brief smoking counseling and medication (offered by both tobacco quitlines and the CET) and the known benefits for quitting smoking for patients with cancer (NCI, 2022), offering to connect patients with cancer who smoke to evidence-based smoking treatment can benefit them. Patients who enter the CET will be offered, at minimum, 2 weeks of nicotine replacement therapy, 3 proactive individual counseling calls, information regarding the Wisconsin Tobacco Quit Line (which also offers individual counseling, 2 weeks of free pharmacotherapy, and digital and remote group support) and

PROTOCOL TITLE: Comparative Effectiveness Trial of Tobacco Cessation Treatments among Cancer Patients who Smoke

the NCI-sponsored SmokefreeTXT program. This exceeds the current standard of care at UW Health (referral to the Wisconsin Tobacco Quit Line). Some participants will be randomly assigned to receive 7 individual sessions and 12 weeks of varenicline. As such, all patients will have access to both pharmacotherapy (if medically appropriate for them) and counseling, whether they enter the CET or elect standard treatment.

For patients who participate in the qualitative interviews and who do not use tobacco, there will be no benefits of participation.

22.0 Risks to Participants

22.1 Risks.

This project poses minimal risk to participants, as it provides only FDA-approved, evidence-based smoking cessation treatment to patients who continue to smoke after cancer diagnosis, and involves minimal risk assessments procedures (providing self-report data and possibly a breath, urine, or saliva sample for biochemical verification of abstinence).

The chief risks to participants include:

- Side effects from medications
 - Nicotine patches can cause skin irritation at the site of application, vivid dreams, and insomnia. Severe allergic reactions are also possible.
 - Common side effects of varenicline include nausea and sleep disturbances. Some people taking varenicline may experience negative moods. Varenicline may also be associated with a small increase in the risk of heart problems in people with heart and blood vessel disease. Rare allergic reactions or skin reactions may occur.
- Psychological discomfort or nicotine withdrawal symptoms. This may occur if participants reduce or quit smoking, and could include negative moods, cigarette cravings, difficulty concentrating, hunger, and problems sleeping. Psychological distress may also be triggered by talking about cancer and cancer care experiences during qualitative interviews.
- Loss of privacy or breach of confidentiality. Although we will not collect sensitive information about participants (apart from cannabis, alcohol, and tobacco use), there is still a risk that participant information may become known to someone

PROTOCOL TITLE: Comparative Effectiveness Trial of Tobacco Cessation Treatments among Cancer Patients who Smoke

not involved in the study, and that this could have negative social or economic consequences for participants.

22.2 Risks associated with participants delaying, being withdrawn from, or being asked to forgo standard treatment to participate in the study.

All patients will have access to evidence-based smoking cessation treatment at no cost (through their primary care provider, oncology care team, a state quit line that offers evidence-based cessation treatment at no cost to callers), or to no-cost treatment through the CET. Receiving treatment is not contingent on consenting to this study. To ensure that smoking treatment does not interfere with ongoing cancer care, oncology clinicians will have the opportunity to review and disapprove medications for patients in the CET. It is also important to note that all participants will have the ability to decline or withdraw from the study and any study activities at any time without jeopardizing access to standard treatment.

22.3 Currently unforeseeable risks. The minimal risk study procedures are unlikely to pose unforeseeable risks to participants.

22.4 Risks to an embryo or fetus. Medications will not be dispensed to people who are pregnant. Smoke cessation counseling poses no risks to embryos or fetuses, whereas continued smoking poses known risks to fetuses.

22.5 Risks to others who are not participants. Study procedures pose no risks to people in participants' lives.

22.6 Strategies to minimize risks of harm or discomfort. Study procedures are designed to protect patient choice and safety, and to ensure that people with impaired decision making will not receive proactive outreach or enrolled in the CET. Participants reached in proactive outreach attempts will be presented standard care options alongside the CET study invitation to protect patient autonomy and choice. Only those who understand and speak English will be eligible for the CET, to ensure they can ask questions and understand study information before and during study enrollment. To protect participant safety, screenings for the CET will exclude people with serious mental illness, recent suicidal behavior, and current suicidal ideation to reduce the risk of psychological distress among participants. Study medications will be dispensed only to people who pass inclusion/exclusion criteria screening and whose clinicians do not deny approval for the medications. Study procedures to monitor adverse events and safety and to protect participant privacy and confidentiality are described elsewhere in this protocol.

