PROTOCOL TITLE: Comparative Effectiveness Trial of Tobacco Cessation Treatments among Cancer Patients who Smoke

- Received care from a participating oncology clinic in the past year.
- Has a current tobacco use status.
- Does not have a preferred language other than English (missing language preference will be included).
- Valid address that is not a correctional facility or residential treatment/care facility.
- No flag for patient cognitive impairment, activated health care power of attorney, or other health care agent (e.g., legally authorized representative) in the EHR.

The following additional inclusion criteria must be met for inclusion in the CET

- Smoked combustible cigarettes in the past month.
- Able to speak and understand English.
- Willing to set a date to quit smoking in the next 60 days.
- Willing to receive smoking treatment information.
- Willing to complete study activities.

For qualitative interviews, the only inclusion criteria are:

- At least 18 years of age.
- Have a history of cancer.
- Willing to participate in an audio-recorded interview about their experiences and perspectives.

5.3 Exclusion criteria. The following exclusion criteria apply to the CET:

- Current suicidal ideation.
- Suicide attempt in the past year.
- Currently receiving treatment for bipolar disorder, schizophrenia, schizoaffective disorder, or psychotic disorder.
- Incarceration.
- Unable to provide informed consent to treatment (i.e., cannot answer questions about study procedures or risks after hearing about the study).

Those who decline the screening invitation or do not meet eligibility criteria will be advised to quit smoking and offered standard smoking cessation treatment (referral to their primary care provider

PROTOCOL TITLE: Comparative Effectiveness Trial of Tobacco Cessation Treatments among Cancer Patients who Smoke

and/or to the Wisconsin Tobacco Quit Line or other tobacco quit line, as appropriate given state of residence).

The only exclusion criterion for qualitative interviews is not being able to provide informed consent due to difficulty understanding the consent information.

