7.3 Recruitment process. Potential tobacco treatment outreach and CET participants will first receive a mailed letter. This letter will inform patients that they have been identified based on their health records for tobacco treatment outreach from UW-CTRI, and will tell them how to opt out of such outreach by calling study coordinators at UW-CTRI. Letters will be sent no more frequently than once per quarter.

Patients who do not opt out of outreach in response to letters will receive up to 5 phone calls per quarter from UW-CTRI study coordinators who will offer tobacco treatment options including both standard care and the CET as available options. Patients can opt out of future outreach at all such phone calls, as well.

Recruitment fliers will also be placed in participating cancer care clinics and/or cancer care providers may give these study invitation fliers to patients interested in participating. These patients may call the study team to learn more about their tobacco treatment options.

Recruitment for qualitative interviews will be conducted by cancer care providers who will have study invitation fliers to give to patients interested in participating. Cancer care providers may also send Health Link InBasket messages to study lead [name] to indicate that the patient is interested and has agreed to receive a call about participating in interviews. In addition, people who are not

PROTOCOL TITLE: Comparative Effectiveness Trial of Tobacco Cessation Treatments among Cancer Patients who Smoke

interested in or eligible for the CET will be asked if they would be interested in participating in the one-time qualitative interview. Participants in the CET will be offered the chance to participate in the qualitative interviews following their 12- and 26-week follow up contacts.

7.4 **Recruitment materials.** The tobacco treatment outreach and CET recruitment letter and an audio version of the recruitment letter is uploaded with the application. These letters will be sent no more frequently than once per quarter during the recruitment period (anticipated to last 2.5 years). The clinic recruitment flier is uploaded with the application.

The script for outreach calls from UW-CTRI study coordinators is also uploaded with the application. Although study coordinators may make up to 5 attempts to reach participants over 12 weeks, this script will be completed only once per quarter with participants.

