Participants may be eligible for a new round of call attempts in future quarters if they appear on a subsequent quarterly CRDS report (and have not already opted out of such calls).

The patient flier and template for Health Link InBasket messages to be used in recruitment for qualitative interviews are uploaded with the application. The script that will be used during interview recruitment calls for referred patients and those who decline or do not meet criteria for the CET is also uploaded with the application.

7.5 **Compensation.** Participants who enroll in the CET will receive pharmacotherapy at no cost (if medically eligible) and will be compensated for completing study assessments according to the following schedule: Baseline phone survey (\$50), 8-week phone follow-up (\$50), 26-week phone follow-up (\$50), biochemical verification of abstinence (\$75 via visit to UW-CTRI for carbon monoxide breath test or urinary cotinine test, or mailed saliva sample kit for cotinine testing). As such, the maximum compensation available to participants will be \$225.

Participants in qualitative interviews will be paid \$40 for completing the interview.

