8.0 Consent/Accent Process

8.1 Informed consent process.

Those who assent to and pass the phone screening for CET participation will be asked to complete an oral consent and HIPAA authorization process in accordance with UW-Madison HRP-090-SOP. This will be completed by phone at the screening call, or at a subsequent call, if necessary. During the phone consent process, a

PROTOCOL TITLE: Comparative Effectiveness Trial of Tobacco Cessation Treatments among Cancer Patients who Smoke

UW-CTRI study coordinator will follow the phone screen and consent script uploaded with the application. These study coordinators will not be involved in patients' ongoing care at UW Health (i.e., this is consent for research and occurs outside of clinical care at UW Health). The consent process will be facilitated by a REDCap database that will conduct automatic validation checks regarding eligibility and will both prompt and document completion of the informed consent process. Participants will have the opportunity to ask questions and to request more information before, during, or after the informed consent process, and they can take time to consider their decision after hearing about the study. They can also elect to receive a written copy of the study information sheet that contains the information covered in the oral consent script before making a decision about participation. Even if they decide to consent without receiving this information in writing, it will be sent to them after the consent is completed by phone. As such, all participants will receive a written study information sheet covering all required elements of informed consent after hearing this information over the phone.

After presenting oral informed consent information, study coordinators will ask a comprehension question to ensure participants understand key components and risks of the study (see uploaded Screening and Consent Script). If participants are still unable to answer these questions correctly after the study coordinator reviews key aspects of the study with them over the phone, the participant will be considered unable to consent. In addition, study coordinators will be trained to monitor for participant understanding during phone contacts and to stop the informed consent process if they have concerns about the participant's mental status or level of comprehension.

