13.0 Procedures Involved

13.1 Study Procedures.

Tobacco treatment outreach. Patients who meet criteria for inclusion on quarterly CRDS reports will first receive a mailed letter informing them that tobacco treatments are available and that quitting smoking has important benefits during cancer care. Patients will also be informed in the letter that they will receive phone outreach from UW-CTRI regarding their tobacco treatment options over the next 12 weeks unless they prefer to opt out of such outreach by calling UW-CTRI to ask that they not receive future tobacco treatment outreach. UW-CTRI study coordinators will make up to 5 attempts to reach patients who do not opt of such calls over 12 weeks. The outreach letter and phone outreach script are uploaded with the application.

Tobacco treatment facilitation. When they reach patients on the phone, UW-CTRI study coordinators will talk with patients about the benefits and challenges of quitting smoking during cancer care and will describe available treatment options (enrolling in Wisconsin Tobacco Quit Line (or other applicable quit line) services; working with their primary or oncology care team; enrolling in the CET) and ask which, if any, treatments the patient would prefer. Patients who decline any treatment will be offered the number of the WTQL/national quit line number. A script for these treatment offers is uploaded with the application.

CET screening. Patients who express interest in the CET will be given information about screening and enrollment procedures and then asked if they assent to eligibility screening. Those who do will complete a brief eligibility screen during the same phone call. Those who do not meet eligibility criteria to continue will be offered quit line services and reminded that their care teams may be able to help them quit smoking, as well. Ineligible participants will also be asked if they would like to participate in a sub-study that involves one phone interview. Those who pass the screening will move on to the oral informed consent process.

Interviews. Up to 32 people, including those who are not eligible or do not enroll in the CET, will be offered an additional \$40 to complete a one-hour telephone interview to gather information that will help improve the way tobacco treatment is offered to people who have had cancer. Participants will first complete an oral consent procedure (uploaded with

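### People screened out of the trial for current suicidal ideation or a past-year suicide attempt are not excepted from the interview invitation, although the plan says the interview may trigger distress

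*Combined protocol and SAP*

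**What the plan says.** Section 5.3 lists current suicidal ideation and a suicide attempt in the past year among the exclusions for the comparative effectiveness trial (CET). Section 22.6 gives the reason: CET screening "will exclude people with serious mental illness, recent suicidal behavior, and current suicidal ideation to reduce the risk of psychological distress among participants".

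Section 13.1 (CET screening) sets out what happens to people who fail screening. They are offered quit line services and "reminded that their care teams may be able to help them quit smoking, as well". It then adds: "Ineligible participants will also be asked if they would like to participate in a sub-study that involves one phone interview". Section 7.3 repeats the rule: people who are not "interested in or eligible for the CET will be asked if they would be interested in participating in the one-time qualitative interview". Section 7.4 mentions a separate script for "interview recruitment calls for referred patients and those who decline or do not meet criteria for the CET".

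Interview eligibility is deliberately broad. Section 5.3 states: "The only exclusion criterion for qualitative interviews is not being able to provide informed consent due to difficulty understanding the consent information". On risk, section 22.1 states: "Psychological distress may also be triggered by talking about cancer and cancer care experiences during qualitative interviews".

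**The concern.** The plan collects an answer that marks a person as someone to be protected from distress. It then routes that person, with no further step in the text, to an invitation for an activity that it names as a possible source of distress. The invitation can come in the same call as the disclosure or in a later recruitment call. The help that sections 5.3 and 13.1 describe for people who fail screening is all about smoking; the protocol body gives no response to the disclosure itself.

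What is at stake is participant safety, and how staff should act when a patient with cancer reports suicidal thoughts. The statistical analysis is not involved.

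**Working it through.** No arithmetic applies, and the plan states no figure to reproduce. The check sets the relevant sections side by side.

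1. **Who is screened out, and why.** Section 5.3 excludes people with current ideation or a past-year attempt from the CET. Section 22.6 ties this to reducing psychological distress.
2. **Who is then invited.** Sections 13.1 and 7.3 both direct the interview invitation to people not eligible for the CET. Neither distinguishes between reasons for ineligibility.
3. **Whether an exception can be inferred.** It cannot. Section 5.3 gives a single interview exclusion, which concerns understanding of the consent information, so suicidality does not bar the interview.
4. **Whether the interview bears on the same hazard.** Section 22.1 says that it may trigger psychological distress, and section 13.1 lists cancer experiences among its topics.
5. **Whether an existing safeguard acts on the known answer before the invitation.**
   - Monitoring for distress and stopping (13.3), and ending early with possible supportive-care referral (15.2), act once the interview has begun.
   - The option to split the interview over several calls (12.1), to decline any question (17.3), and to withdraw and have the recording destroyed (15.3) give the interviewee control, but they also come after the invitation.
   - Under section 8.1, coordinators are trained to "stop the informed consent process if they have concerns about the participant's mental status or level of comprehension". This could act before exposure, but it is written in the account of CET consent. The same section gives interviewees their own oral consent and does not say that this stop carries over.
   - The standardized adverse-event prompts in section 23.1 run at CET contacts 2 to 11, which a person who only does the interview never has.
6. **Whether this recruitment route differs from the others.** It does. CET participants invited after their 12- and 26-week follow-ups passed the suicidality screen at entry. Patients referred by their cancer team are not asked about suicidality in the visible text, and people who decline before screening may never be asked. Only on the screen-failure route do study staff already hold a positive answer when the invitation falls due.

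Steps 1 to 4 establish the gap. Step 5 shows that nothing in the protocol text closes it before the invitation. Step 6 shows that it can be closed without a new question.

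**The case against.** The strongest reply is that the two parts of the study expose people to different things. The section 22.6 reason is written for CET screening. The CET involves a quit attempt and, for most, medication, over up to 8 months, and section 22.1 links negative mood to both withdrawal and varenicline. The interview lasts about an hour, is voluntary, needs its own consent, and is described in section 8.2 as no more than minimal risk. Section 5.1 calls its eligibility criteria minimal, and section 6.2 explains why vulnerable groups are not kept out. Different criteria for different exposures are legitimate. This stands, and it defeats any claim that the plan contradicts itself.

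Second, what staff say to someone who fails screening is in uploaded scripts that are not part of these documents, and a response to disclosed ideation may well be there. This also stands. A reader might infer that the study has no procedure for a suicidality disclosure; the documents support only that the protocol body states none. Nor should a reader infer that interviewees have no protection from distress: the safeguards in 12.1, 13.3, 15.2, 15.3 and 17.3 are real.

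Third, a change limited to suicidality leaves neighbouring cases untouched. Section 22.6 gives the same reason for excluding serious mental illness, and clinic-referred interviewees are not visibly screened at all. That is fair, and those cases need a decision. It does not justify ignoring the one route on which the answer is already known.

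**Conclusion.** The point holds as a small participant-safety gap in the protocol text. Sections 13.1 and 7.3 direct an interview invitation to people screened out for current suicidal ideation or a past-year attempt, without exception, while 22.6 and 22.1 together show that the plan regards distress as a hazard both for these people and in this activity.

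Its size cannot be estimated. The documents give no count of people screened and no rate of suicidality, so a probability would only restate whatever rates were assumed. The number is probably very small. What is counted would be invitations, not interviews or harms; a reader might infer that harm is likely, and nothing in the documents supports that. No estimate, endpoint or analysis is affected.

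The conclusion assumes that the uploaded scripts do not already contain an exception. If they do, the remaining task is to bring the protocol text into line with them. This is a matter for the sponsor to consider, not a condition for running the study.

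**What to change.** Add to sections 13.1 and 7.3 that people screened out of the CET for current suicidal ideation or a suicide attempt in the past year are not routinely offered the interview at that contact and are directed to their care team. Match the screening script and the interview recruitment script named in section 7.4. If the scripts already handle this, bring the protocol into line with them.

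Leave three decisions to the investigator and the IRB: whether this group may be offered the interview later; how to handle people excluded for serious mental illness, for whom section 22.6 gives the same reason; and whether other interview recruitment routes need any screening.

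The cost is wording and script changes. No new question is needed, because CET screening already has to establish the answer. A few fewer people would be invited, some of this group's views may be lost, and a voluntary option would not be routinely open to them. The loss to the substudy should be small: 32 interviews is an upper limit, section 4.2 expects saturation below it, and the same section says that as few as 2 to 5 interviews could be useful. CET enrolment and analysis are unchanged.
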